Prior to re-treatment with study drug, patients will be evaluated for the following conditions and laboratory abnormalities. If any of these are present prior to re-dosing,

further administration of study drug should be suspended until these are resolved or held indefinitely:

Life-threatening (Grade 4) infusion-related event that occurred during a previous study drug infusion

Any significant or uncontrolled medical condition or treatment-emergent, clinically significant laboratory abnormality

Active infection

Ongoing pregnancy

Investigational Medicinal Product Accountability

All IMPs required for completion of this study (ocrelizumab/placebo) will be provided by Genentech where required by local health authority regulations. The study site will acknowledge receipt of IMPs supplied by Genentech, using the IxRS to confirm the shipment condition and content. Any damaged shipments will be replaced.

IMPs will either be disposed of at the study site according to the study site's institutional standard operating procedure or be returned to the drug depot with the appropriate documentation. The site's method of destroying Genentech-supplied IMPs must be agreed to by the Sponsor. The site must obtain written authorization from the Sponsor before any IMP is destroyed, and IMP destruction must be documented on the appropriate form.

Accurate records of all IMPs received at, dispensed from, returned to, and disposed of by the study site should be recorded on the Drug Inventory Log.

Continued Access to Ocrelizumab

Currently, Genentech, a member of the Roche Group, does not have any plans to provide Genentech IMP (ocrelizumab) or any other study treatments to patients beyond the second-year extension of the study or the 2 year sub-study. Genentech may evaluate whether to continue providing ocrelizumab in accordance with the Roche Global Policy on Continued Access to Investigational Medicinal Product, available at the following website:

http://www.roche.com/policy_continued_access_to_investigational_medicines.pdf

CONCOMITANT THERAPY

Concomitant therapy consists of any medication (e.g., prescription drugs, over-the-counter drugs, vaccines, herbal or homeopathic remedies, nutritional supplements) used by a patient in addition to protocol-mandated treatment from 7 days

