RBR samples will be tracked in a manner consistent with Good Clinical Practice by a quality-controlled, auditable, and appropriately validated laboratory information management system, to ensure compliance with data confidentiality as well as adherence to authorized use of samples as specified in this protocol and in the Informed Consent Form. Sponsor monitors and auditors will have direct access to appropriate parts of records relating to patient participation in the RBR for the purposes of verifying the data provided to the Sponsor. The site will permit monitoring, audits, IRB/EC review, and health authority inspections by providing direct access to source data and documents related to the RBR samples.

TREATMENT, PATIENT, AND STUDY DISCONTINUATION

Study Treatment Discontinuation

Patients must permanently discontinue study treatment if they experience any of the following:

Any medical condition that the investigator or Sponsor determines may jeopardize the patient's safety if he or she continues to receive study treatment

Investigator or Sponsor determination that treatment discontinuation is in the best interest of the patient

Additionally, patients must be withdrawn from treatment under the following circumstances:

Life-threatening (National Cancer Institute Common Terminology Criteria for Adverse Events [NCI CTCAE] Grade 4) infusion-related event that occurred during a previous ocrelizumab infusion

Demonstrate active hepatitis B infection, either new onset or reactivation

PML

Newly diagnosed malignancy

Patients who become pregnant /or lactating

Patients who decide to discontinue treatment

The primary reason for study treatment discontinuation should be documented on the appropriate eCRF. Patients who discontinue study treatment prematurely will not be replaced.

If a patient meets any of the treatment withdrawal criteria (see above), the patient must be withdrawn from treatment. Patients who prematurely withdraw from study drug treatment will need to return to the clinic for an unscheduled treatment discontinuation visit (see Appendix 1 for additional details). After treatment discontinuation, every effort should be made to have the patient enter the follow-up phase of the study.

For patients who have withdrawn from study drug treatment, the investigator should decide as to further treatment of the underlying disease (see Section 4.4 for recommendations on alternative treatments for MS post-ocrelizumab).

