Hypersensitivity may be difficult to distinguish from IRRs in terms of symptoms. A hypersensitivity reaction may present during any infusion, although typically would not present during the first infusion. For subsequent infusions, more severe symptoms than previously experienced, or new severe symptoms, should prompt consideration of a potential hypersensitivity reaction. If a hypersensitivity reaction is suspected during infusion, the infusion must be stopped immediately and permanently. Patients with known IgE-mediated hypersensitivity to ocrelizumab must not be treated.

Malignancies (including Breast Cancer)

An increased risk of malignancy with OCREVUS may exist. In controlled trials in MS, malignancies, including breast cancer, occurred more frequently in OCREVUS-treated patients. Breast cancer occurred in 6 of 781 females treated with ocrelizumab and none of 668 females treated with REBIF or placebo. Patients should follow standard breast cancer screening guidelines.

Refer to the current Ocrelizumab Investigator's Brochure for more details.

Neutropenia

In the controlled treatment period, decreased neutrophils were observed in 12% and 15% of MS patients treated with ocrelizumab in PPMS and RMS, respectively. Most were mild to moderate in severity, approximately 1% of the patients had Grade 3 or 4 neutropenia; and no temporal association with infections was identified. Based on

additional patient exposure, an association between neutropenia and serious infections with ocrelizumab treatment was not observed.

Additional information can be found in the current Ocrelizumab Investigator's Brochure.

Risks Associated with Corticosteroids

The adverse reactions of corticosteroids may result from unwanted glucocorticoid actions or from inhibition of the hypothalamic-pituitary-adrenal axis. Please refer to local prescribing information.

Risks Associated with Antihistamines

The adverse reactions depend on the sedating properties of the antihistamine and include, but are not limited to, nausea, drowsiness, headaches, dry mouth, and allergic reactions such as rash. Please refer to local prescribing information.

Management of Patients Who Experience Adverse Events

Dose Modifications

Study drug dose modifications are not foreseen.

Treatment Interruption

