Study drug treatment may be temporarily suspended in patients who experience relevant adverse events considered to be related to study drug and prevent the patient from re-treatment with the study drug (see Section 4.3.2.3 for details on re-treatment criteria).

For female patients who become pregnant during the study, study drug treatment will be discontinued upon confirmation of pregnancy. Study drug will not be re-started, but the patient should continue with other study-related visits and assessments, unless they are contraindicated due to pregnancy.

Management Guidelines Infusion-Related Reactions

Slowing of the infusion rate or interruption of the infusion may be necessary in the event of an infusion reaction. In rare cases, ocrelizumab treatment may need to be discontinued. Please also follow ocrelizumab local label for further guidelines.

Handling of IRRs will depend on the intensity of symptoms (see also Table 2 for grading of intensity of IRRs).

For a **mild to moderate (Grade 1 or 2)** non-allergic, infusion-related event, the infusion rate should be reduced to half the rate being given at the time of onset of the event (e.g., from 50 mL/hr to 25 mL/hr or from 100 mL/hr to 50 mL/hr). Once the event has resolved, the investigator should wait for 30 minutes while delivering the infusion at the reduced rate. If tolerated, the infusion rate may then be increased to the next closest rate on the patient's infusion schedule and the rate increments resumed.

For a **severe infusion-related event (Grade 3)** or a complex of flushing, fever, and throat pain symptoms, the infusion should be interrupted immediately and the patient should receive aggressive symptomatic treatment. The infusion should be restarted only after all the symptoms have disappeared. The initial infusion rate at restart should be half of the infusion rate that was in progress at the time of onset of the reaction.

For a **life-threatening infusion-related event (Grade 4)** during an infusion, the infusion should be immediately stopped, and the patient should receive appropriate treatment (including use of resuscitation medications and equipment that must be available and used as clinically indicated). The patient will be withdrawn from treatment and should enter the follow-up phase.

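### Read alone, Section 4.3.2.3 allows re-dosing once a pregnancy has ended, while other sections require withdrawal with no restart; it also leaves the outcome of a Grade 4 infusion reaction open

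*Combined protocol and SAP*

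**What the plan says.** Four parts of the protocol deal with these conditions.

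- **Section 4.3.2.3, Re-Treatment Criteria for Ocrelizumab.** Patients are checked before re-treatment for four conditions. If any is present, "further administration of study drug should be suspended until these are resolved or held indefinitely". Two of the four are "Life-threatening (Grade 4) infusion-related event that occurred during a previous study drug infusion" and "Ongoing pregnancy". The section does not say which of the two outcomes belongs to which condition, and it does not refer to the discontinuation rules.
- **Study Treatment Discontinuation (Section 4.6).** This section states that "patients must be withdrawn from treatment under the following circumstances". Its list includes a Grade 4 infusion-related event at an earlier infusion, and becoming pregnant or lactating. It then repeats that anyone meeting a criterion has to be withdrawn.
- **Management of Patients Who Experience Adverse Events (Section 5.1).** Under Treatment Interruption, study drug is discontinued once pregnancy is confirmed: "Study drug will not be re-started, but the patient should continue with other study-related visits and assessments". Under the infusion-reaction guidelines, for Grade 4: "The patient will be withdrawn from treatment and should enter the follow-up phase".
- **Overview of Clinical Visits (Section 4.5).** Patients who are pregnant or breastfeeding keep to the visit schedule without infusions. Nothing is said about dosing afterwards.

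**The concern.** The re-treatment criteria are what a site applies when deciding whether to give the next infusion. The Blinding section describes a pre-infusion check of pre-specified conditions, the Overview of Clinical Visits makes a next-day infusion depend on the re-treatment criteria, and Treatment Interruption refers to 4.3.2.3 for temporary suspension. If that list reads as more permissive than the discontinuation rules, a site relying on it could resume dosing in a patient whom another section takes off treatment for good.

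What is at stake is mainly patient safety and consistent conduct across sites: re-exposure after a pregnancy or after a life-threatening infusion reaction. A secondary effect is that the number of courses such a patient receives could depend on which section the site consulted.

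**Working it through.** No arithmetic applies. The check is to follow each condition through every section that governs it.

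**Pregnancy**

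1. Section 4.3.2.3 lists "Ongoing pregnancy". The adjective ties the condition to the present. Once the pregnancy ends, the listed condition is absent and the suspended-until-resolved branch is satisfied.
2. Study Treatment Discontinuation lists becoming pregnant. This is triggered by the event and has no exception for a pregnancy that has ended.
3. Treatment Interruption bars a restart: "Study drug will not be re-started, but the patient should continue with other study-related visits and assessments".
4. The Overview of Clinical Visits stops infusions during pregnancy or breastfeeding and is silent on what follows.

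Take a hypothetical patient whose pregnancy is confirmed at Week 28 and has ended by Week 40. At the Week 48 infusion, item 1 permits re-dosing, items 2 and 3 rule it out, and item 4 does not decide. This is a direct conflict.

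Breastfeeding shows a milder version. The discontinuation list makes lactation a withdrawal, the visit overview words it as a bar on infusions while it lasts, and 4.3.2.3 does not name it. All agree, or are silent, on dosing during breastfeeding; its status afterwards is not stated consistently.

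**Grade 4 infusion-related event**

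1. Section 4.3.2.3 lists "Life-threatening (Grade 4) infusion-related event that occurred during a previous study drug infusion" under the same either/or rule.
2. Study Treatment Discontinuation lists nearly the same event as a mandatory withdrawal.
3. The infusion-reaction guidelines repeat it: "The patient will be withdrawn from treatment and should enter the follow-up phase".

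The conflict exists only on the until-resolved branch. The item describes something that happened at an earlier infusion, so it can be read as permanently true, leaving only the indefinite hold, which agrees with items 2 and 3. The section does not say so. Nor is permanence spelled out in the discontinuation section for this item: the word permanently introduces the preceding list. Permanence for Grade 4 is inferred from withdrawal plus entry to follow-up.

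**Result.** Two of the four re-treatment items have a different status elsewhere. One conflict is direct (pregnancy); the other depends on which branch is read (Grade 4). The sections cited state no order of precedence.

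**The case against.** The strongest reply is that a site applying the whole protocol has no real choice. Withdrawal is mandatory in Section 4.6 and repeated there, the bar on restarting after pregnancy is explicit in Section 5.1, and 4.3.2.3 offers an indefinite hold that is compatible with both. It permits resumption on one branch but nowhere directs it. The dosing section that contains 4.3.2.3 also points to Section 5.1.4 for interruption and discontinuation.

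Much of this stands. A site that re-dosed would breach other sections, so it would go too far to infer that two sites can each comply fully and act in opposite ways. But an option to hold indefinitely is not a requirement to withdraw. The pointer to 5.1.4 is worded for patients with adverse events, while the safety-reporting section says pregnancy reports are not in themselves serious adverse events or reactions, so the pointer may not lead a site to the pregnancy rule. And Treatment Interruption refers back to 4.3.2.3.

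A reader might infer more than the documents support:

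- **That a breastfeeding patient could be dosed because 4.3.2.3 omits lactation.** The Overview of Clinical Visits rules out infusions during breastfeeding, and the discontinuation list covers lactation.
- **That suspected hypersensitivity, or the restart rule for Grade 3 reactions, adds a contradiction.** Hypersensitivity has its own rule, "If a hypersensitivity reaction is suspected during infusion, the infusion must be stopped immediately and permanently", and absence from another list does not contradict it. The infusion-reaction guidance also defers to product labelling that is not in the documents.
- **That the scale is every pre-infusion check in the trial.** Counting checks says nothing about how many involve either condition.

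**Conclusion.** The point stands as an internal inconsistency, not as a criticism of a design choice. For pregnancy, 4.3.2.3 read alone allows what Study Treatment Discontinuation and Treatment Interruption exclude. For a Grade 4 infusion-related event the conflict is softer: 4.3.2.3 fails to assign an outcome that the other sections make mandatory.

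The number affected should be small. Women of childbearing potential must agree to abstinence or contraception, those intending pregnancy during treatment are excluded, and the last scheduled infusion is at Week 48, so on the planned schedule a pregnancy has to begin and end before a remaining infusion for the conflict to arise. The documents give no expected rate of pregnancy or Grade 4 reactions in this population, so no count is offered.

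The primary analysis is not at risk. It follows a treatment-policy strategy over all randomized patients regardless of adherence, and a few changed courses would matter little. The case for acting rests on patient safety and uniform conduct. It assumes that sites use 4.3.2.3 as the pre-infusion check, as the cross-references suggest. No view is taken on which clinical rule is right.

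**What to change.** Reconcile Section 4.3.2.3, the Overview of Clinical Visits, Study Treatment Discontinuation, and the Treatment Interruption and Grade 4 infusion-reaction text in Section 5.1:

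- Give pregnancy (with breastfeeding) one status, either temporary hold or permanent withdrawal, in identical words wherever it appears.
- Do the same for a Grade 4 infusion-related event at an earlier infusion.
- In 4.3.2.3, separate conditions that are temporary holds from those that are not, and refer to the discontinuation section for the latter.

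The sponsor's clinical team decides which status applies to each condition. The cost is a wording amendment to these sections, with matching changes to any site material derived from them. No procedures, visits or patients are added, and the sample size and analysis are unchanged.

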Change from Baseline to Weeks 104 and 208 in CSF biomarkers (i.e., CSF Weeks 104 and 208 only), including CXCL13, BAFF (B cell activating factor), TNF, IL-6, IL-10, IL-17, interferon-gamma, IL-4, IL-23, IL-8, soluble CD27 (sCD27), genetic risk factors (HLA-DRB1*15:01) or other emerging exploratory markers of disease biology as appropriate

Change from Baseline to Weeks 48, 104, and 208 in slowly evolving lesions (SEL)

Change from Baseline to Weeks 24, 48, 72, 104, 130, 156, 182 and 208 in peripheral blood immune cell population frequency and phenotype, including B cells, T cells and innate immune cells (monocyte, macrophage, neutrophils, natural killer cells, etc.)

Change from Baseline to Weeks 24, 48, 72, 104, 130, 156, 182 and 208 in peripheral blood biomarkers, including CXCL13, BAFF (B cell activating factor), TNF, IL-6, IL-10, IL-17, interferon-gamma, IL-4, IL-23, IL-8, soluble CD27 (sCD27), genetic risk factors (e.g., HLA-DRB1*15:01) or other emerging exploratory markers of disease biology as appropriate

Change from Baseline to Weeks 24, 48, 72, 104, 130, 156, 182 and 208 in patient reported outcomes, including quality of life, fatigue, depression, and disability, as measured by Neuro-QoL™

Change from Baseline to Weeks 24, 48, 72, 104, 130, 156, 182 and 208 in cognitive function and information processing speed as measured by symbol digit modality test (SDMT)

Correlation between changes in compartment-specific biomarkers of disease biology with radiologic and/or clinical disease outcomes

Correlation between changes in patient reported outcomes, including SDMT, and radiologic and/or clinical disease outcomes

Correlation between changes in compartment-specific immune cell subsets with radiologic and/or clinical disease outcomes.

Correlation between changes in NfL levels and radiologic and/or clinical disease outcomes

Correlation between changes in CSF abnormalities (OCB and IgG index) and radiologic and/or clinical disease outcomes

SAFETY OBJECTIVES

The safety objectives for this study are to evaluate the safety of ocrelizumab compared with placebo on the basis of the following endpoints:

Nature, frequency, severity, and timing of adverse events

Vital signs, physical findings, and clinical laboratory results during and following study drug administration

Adverse events related to biomarker sample collection

STUDY DESIGN

DESCRIPTION OF THE STUDY

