On the infusion days, blood pressure, pulse rate, and temperature should be taken within 45 minutes prior to the premedication (methylprednisolone) infusion and recorded on the appropriate eCRF. Temperature should be measured and recorded in patient's notes only.. Vitals will be monitored during infusions of study drug according to the prescribing information. Clinically significant abnormalities should be recorded on the Adverse Event or Infusion-Related Reaction. In the event of an IRR or if clinically indicated, additional vital signs readings (e.g., blood pressure and pulse rate) should be taken during and post-infusion at the discretion of the investigator and should be recorded on a dedicated Vital Sign eCRF.

Neurological Examination

A neurological examination will be performed at every planned visit. During an unscheduled visit, the neurological examination will be performed only if deemed necessary.

In the presence of newly identified or worsening neurological symptoms at any given time in the study, a neurological evaluation should be scheduled promptly and performed within 7 days of onset of the new or worsening neurological symptom(s).

Study investigators will screen patients for signs and symptoms of PML through evaluation of neurological deficits localized to the cerebral cortex, such as cortical symptoms/signs, behavioral and neuropsychological alteration, retrochiasmal visual defects, hemiparesis, and cerebellar symptoms/signs (e.g., gait abnormalities, limb incoordination). A brain MRI scan and CSF analysis may be warranted to assist in the diagnosis of PML. Refer to Appendix 7 for guidance on the diagnosis of PML.

Patients with suspected PML, defined as a new or worsening neurological symptom that necessitates MRI and/or lumbar puncture and CSF analyses to rule out PML, should be withheld from study treatment until PML is ruled out by complete serial clinical evaluations and appropriate diagnostic testing (see Appendix 7). The Medical Monitor should be immediately contacted by telephone and email.

A patient with confirmed PML should be withdrawn from treatment. PML should be reported as a serious adverse event (with all available information) with immediate notification of the Medical Monitor (see also Section 5.1.1.2).

Brain and Cervical Spine Magnetic Resonance Imaging

Pre-screening of family members:

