Several measures will be taken to ensure the safety of patients participating in this study. Eligibility criteria have been designed to exclude patients at higher risk for toxicities. Patients will undergo safety monitoring during the study, including assessment of the nature, frequency, and severity of adverse events. In addition, guidelines for managing adverse events, including criteria for dosage modification and treatment interruption or discontinuation, are provided below.

Risks Associated with Ocrelizumab

Important, identified, and potential risks associated with ocrelizumab are described in the approved risk management plan, and provided below. Please refer to the most recent version of the Ocrelizumab Investigator's Brochure for updates on risks associated with ocrelizumab treatment.

Identified Risks and Adverse Drug Reactions

Infusion-Related Reactions

All CD20-depleting agents administered via the intravenous route, including ocrelizumab, have been associated with acute IRRs. Following the approved administration regimen (which includes the use of premedication prior to treatment with ocrelizumab to reduce frequency and severity of IRRs), symptoms of IRRs may occur during any ocrelizumab infusion, but have been more frequently reported during the first infusion. Physicians should alert patients that IRRs can occur within 24 hours of the infusion. Across the RMS and PPMS trials, symptoms associated with IRRs included, but are not limited to the following: pruritus, rash, urticaria, erythema, bronchospasms, throat irritation, oropharyngeal pain, dyspnea, pharyngeal or laryngeal edema, flushing, hypotension, pyrexia, fatigue, headache, dizziness, nausea, tachycardia, and anaphylaxis.

Patients should be observed for at least 1 hour after the completion of the infusion for any symptom of IRR. Patients will be informed about delayed post-infusion symptoms and instructed to contact the study physician if he or she develops such symptoms.

Hypotension, as a symptom of IRR, may occur during ocrelizumab infusions. Therefore, withholding of antihypertensive treatments should be considered for 12 hours prior to and throughout each ocrelizumab infusion.

For further guidance on how to manage IRRs please refer to the current Ocrelizumab Investigator's Brochure.

Infections

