Population-level-summary estimator: The hazard ratio from a stratified Cox-proportional hazards model will be used. The stratified log-rank p-value will be used to test for statistical significance. Both will be stratified by the factors specified (see Section 4.2.1) for randomization.

Handling of missing data:

Withdrawal from study: a patient will be censored at the time of withdrawal from study.

Missing assessments at scheduled visits prior to last assessment: Missing data at scheduled visits prior to last assessment will not be imputed.

Secondary Efficacy Endpoints

The secondary endpoints for this study are to evaluate the efficacy and impact of ocrelizumab compared with placebo on the basis of the endpoints as described in Section 2.2.1 and biomarkers of disease activity and neuroaxonal damage in peripheral blood.

Each change from baseline for continuous secondary endpoints will be tested and analyzed using a stratified mixed-effects model for repeated measures (MMRM)

assuming missing at random (MAR). Sensitivity analyses will be conducted to assess the validity of this assumption,

For MRI related count endpoints (cumulative number of T2 lesions and T1 gadolinium-enhancing lesions), generalized linear methods appropriate for count data will be used depending on the distribution of the counts, e.g., a stratified negative binomial regression model.

Estimands for the Secondary Analyses

The estimands for the remaining secondary endpoints will have the same population and handling of missing data attributes as for the primary analysis.

Exploratory Efficacy Endpoints

Analyses on exploratory efficacy endpoints will be performed as data allows.

Exploratory efficacy endpoints are listed in Section 2.2.2. Further details will be described in the SAP.

SAFETY ANALYSES

The safety analysis population will consist of all randomized patients who received at least one dose of study drug, with patients grouped according to treatment received.

Safety will be assessed through summaries of exposure to study treatment, adverse events, changes in laboratory test results, and changes in vital signs and ECGs. Study treatment exposure (such as treatment duration, total dose received, and number of cycles and dose modifications) will be summarized with descriptive statistics.

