* If these assessments have been completed during the pre-screening evaluation for an individual who is subsequently found to meet study criteria and enrolled in the main study, they do NOT need to be repeated during the Screening and/or Baseline Visits, as long as those visits take place within 6 weeks of the pre-screening assessment.

^a The screening window is up to 45 days prior to baseline and all screening and baseline assessments must be conducted prior to first dose.

^b In the case of a neurological event consistent with CNS demyelination during the study, the patient should have an unscheduled visit and all assessments completed. An MRI may be optionally performed at this visit if clinically indicated. If the patient comes into the clinic for an unscheduled visit for reasons other than relapse, procedures should be performed per standard of care.

^c In the case of early termination, the patient will be asked to return for an early termination visit/ study discontinuation visit, at which time all assessments must be completed/obtained, except MRI if done within the past 8 weeks, unless clinically indicated.

^d Written informed consent will be obtained from all patients during screening in order to be eligible.

^e Medical history includes clinically significant diseases, surgeries, reproductive status, smoking history, and all medications (e.g., prescription drugs, over-the-counter drugs, herbal or homeopathic remedies, and nutritional supplements) used by the patient within 4 weeks prior to the screening visit. In addition, any previous MS medication should be recorded. Demographic data will include age, sex, and self-reported race/ethnicity.

^f Vital signs will include measurements of heart rate, systolic and diastolic blood pressure, and temperature. Vital signs should be taken approximately 45 minutes prior to premedication.

^g After the screening visit, only weight will be measured.

^h A full physical examination will be conducted at the screening and early termination visits. At all other visits, a limited physical examination will be conducted. Any abnormality identified at baseline should be recorded on the eCRF. Changes from baseline abnormalities should be recorded at each subsequent physical examination. New or worsened clinically significant abnormalities should be recorded as adverse events, if appropriate.

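### Infusion-time vital signs are entered on the eCRF only for a reaction or a clinical indication, so their changes cannot be compared between arms without selection; the temperature and ECG wording also needs reconciling

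*Combined protocol and SAP*

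**What the plan says.** The Safety Objectives list this endpoint, separately from adverse events: "Vital signs, physical findings, and clinical laboratory results during and following study drug administration". The Safety Analyses section says that safety will be assessed through, among other things, "changes in laboratory test results, and changes in vital signs and ECGs".

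The Vital Signs section under Study Assessments sets out what is measured and where it goes:

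- For every patient: "On the infusion days, blood pressure, pulse rate, and temperature should be taken within 45 minutes prior to the premedication (methylprednisolone) infusion", with entry on the eCRF.
- The next sentence: "Temperature should be measured and recorded in patient's notes only".
- During infusion: "Vitals will be monitored during infusions of study drug according to the prescribing information". No timepoints are given, and no form is named for ordinary readings.
- Abnormalities judged clinically significant go to the adverse event or infusion-related reaction record.
- "In the event of an IRR or if clinically indicated, additional vital signs readings" are taken during and after the infusion if the investigator so decides, and entered on a separate Vital Sign eCRF. The examples given are blood pressure and pulse.

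Appendix 1, footnote f, gives the only timing rule in the schedule: "Vital signs should be taken approximately 45 minutes prior to premedication". The schedule also lists vital signs at the visits without infusion, through Week 208. The section on infusion-related reactions says: "Hypotension, as a symptom of IRR, may occur during ocrelizumab infusions". It also names fever and tachycardia among the symptoms.

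**The concern.** The acute effects of the drug on blood pressure, pulse and temperature are expected around the infusion. The readings required on an eCRF for everyone are taken before that window opens. The readings inside the window enter the database only when someone has recognised a reaction or sees a clinical reason to record them.

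Recording is then a post-randomization event that treatment can influence. A table of changes built on those readings would compare one selected group of ocrelizumab patients with a differently selected group of placebo patients. Both arms receive methylprednisolone and an antihistamine, so separating drug from premedication effects on vital signs needs readings collected in the same way in both arms. Values that never reached the database cannot be recovered at the analysis stage.

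**Working it through.** The plan states no figure on this point and no power formula applies. The check is a count and a side-by-side reading.

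1. **Infusion visits.** Weeks 0, 2, 24 and 48, so 4 per patient. With about 100 patients and complete dosing, 100 × 4 = 400 infusion visits.

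2. **Vital-sign readings with a required eCRF entry for every patient, per infusion visit** (Vital Signs section; footnote f). Before premedication: 1. During infusion: 0. After infusion: 0.

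3. **What a change from baseline can show with the required readings.** Nominal distance from the preceding infusion, before visit windows:
   - Week 2: 2 − 0 = 2 weeks
   - Week 24: 24 − 2 = 22 weeks
   - Week 48: 48 − 24 = 24 weeks
   - Week 72, the first visit after treatment: 72 − 48 = 24 weeks

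   No required reading lies closer than about 2 weeks after an infusion. These data can describe longer-term change, but not change during the infusion.

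4. **What the conditional readings can show.** Among recorded patients, the difference between arms is a difference conditional on being recorded. It equals the effect of treatment only if recording is unrelated to the readings, and the recording rule makes it depend on them.

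5. **What is captured elsewhere.** Clinically significant abnormalities go to the adverse event or infusion-related reaction record. The Safety Analyses section summarizes treatment-emergent events by term and grade, with patients grouped by treatment received. What is not available for all patients is the size of the infusion-time change, including changes not called clinically significant.

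6. **The timing phrase in the Safety Objectives has two readings.**
   - As the infusion: Appendix 1 marks its study drug administration row only at Weeks 0, 2, 24 and 48, and its footnotes time samples relative to administration on the day. On this reading the endpoint is not systematically measured.
   - As the treatment and follow-up periods: the phrase also governs physical findings and laboratory results, and no laboratory test is scheduled during an infusion. On this reading the scheduled visits supply the endpoint.

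7. **Temperature.** Two consecutive sentences in the Vital Signs section send it to the eCRF and then to the notes alone. The same section and footnote f both count temperature as a vital sign. If the second sentence governs, no temperature value is available for the vital-sign summary.

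8. **Timing of the pre-infusion reading.** The Vital Signs section sets an upper limit of 45 minutes before premedication; footnote f sets an approximate time of 45 minutes before it.

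9. **ECGs.** Number of ECG rows in Appendix 1: 0. The promised summary of ECG changes has no scheduled data source.

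**The case against.** The strongest reply is that the endpoint may concern study periods and not the infusion. The phrase covers laboratory results too, and for these only the wider meaning makes sense. This stands as a possible reading, and it is why the conclusion is conditional on that point. It does not remove the temperature contradiction or the missing ECG source.

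A second reply is that acute harm is already covered. A reader might infer that infusion hypotension or fever will go unseen. The documents do not support that: clinically significant cases appear by arm in the adverse event tables, and triggered readings have their own eCRF. Nor are infusion readings confined to reactions, because clinical indication is a separate trigger. The statement about pre-premedication readings applies to infusion days only, since vital signs are also scheduled at later visits.

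A third reply is that non-recording of ordinary readings is inferred from silence, as neither the eCRF nor the prescribing information is part of the documents. That is fair. The protocol names no form for ordinary during-infusion readings and names one for triggered readings, but the eCRF could be wider than the protocol.

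Finally, a reader might want to state how many infusions would contribute no reading. The documents give no reaction rate for this population and no rate of clinically indicated readings, so no such number can be derived.

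**Conclusion.** The point holds as a modest gap in safety data collection. On infusion days one reading per visit, before premedication, is required on an eCRF for every patient. During-infusion values enter conditionally, so their changes cannot be compared by arm without selection. Clinically significant abnormalities remain captured as adverse events or infusion-related reactions.

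Whether a stated endpoint goes unmeasured depends on what the Safety Objectives mean by administration. If they mean the infusion, it is not systematically measured. If they mean the treatment and follow-up periods, the wording should say so. The conflicting temperature sentences and the ECG summary without scheduled data hold on either reading.

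The conclusion assumes that the eCRF follows the protocol text. It does not touch the primary or secondary efficacy analyses, and correcting it is a low-cost improvement.

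**What to change.** - In the Vital Signs section, require that the during-infusion readings already taken under the prescribing information be entered on the existing Vital Sign eCRF for all patients at the four infusion visits. Examples are the lowest systolic pressure and highest pulse, plus temperature where it is measured.
- In Safety Analyses, summarize the change from the pre-premedication value by arm and infusion number.
- In the Safety Objectives, say whether the timing phrase means the infusion or the treatment and follow-up periods.
- Reconcile the two temperature sentences so that it is clear whether temperature enters the database for the vital-sign summary. Reconcile the two 45-minute timings as well.
- Reconcile Safety Analyses with Appendix 1 on ECGs. Which way this is settled is for the sponsor.

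The change should not presume readings at the 1-hour observation: the protocol requires patients to be observed then but does not say that vital signs are measured.

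The cost is data entry at four visits per patient, up to 100 × 4 = 400 entries with complete dosing, and one table. If the change is limited to readings already taken, no new assessment is added.
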